We propose to study the effects of a randomized exercise intervention on DSP outcomes (Aim 1). We will recruit patients from a Bariatric Surgery clinics. Patients will be recruited after their visit with the physician's assistant and/or surgeon. We will stratify randomization of the exercise intervention by those that do and those that do not have bariatric surgery to allow evaluation of the effect of surgical weight loss on DSP outcomes (Aim 2). For the exercise intervention, we will employ the *innovative* high intensity interval training (HIIT) regimen, which our group has shown improves metabolic outcomes and has high compliance. For weight loss, bariatric surgery results in larger and more sustained weight loss compared to dietary approaches, making this an ideal intervention to investigate. Similar to HIIT, surgical weight loss improves metabolic outcomes and has high compliance.

Aim 1: Examine the efficacy of a HIIT exercise regimen on DSP outcomes (randomized). We hypothesize that HIIT will improve DSP outcomes compared with routine exercise counseling. To test this hypothesis, we will randomize patients approved for bariatric surgery clinic 1:1 to HIIT versus routine exercise counseling. The HIIT regimen will consist of 3 sessions/week (2 supervised and 1 unsupervised) for 24 months. Routine exercise counseling is the current real world practice in the bariatric surgery clinic. The primary DSP outcome will be intraepidermal nerve fiber density (IENFD) of the proximal thigh measured at baseline, 3, 12, and 24 months. Linear mixed models will determine the longitudinal effect of HIIT on DSP while accounting for repeated measures. Importantly, we will capture a sensitive, quantitative DSP measure (IENFD), determine if an intervention effect exists, and link the measures to meaningful patient-oriented outcomes such as DSP-related pain (Short form McGill), function (Berg Balance Scale), and quality of life (NeuroQOL).

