Exercise compliance: In addition to the 2 supervised sessions per week, subjects will be asked to complete 1 unsupervised session. To improve compliance in both types of sessions, patients will receive monthly phone calls from research staff to discuss potential solutions to barriers. Subjects will be provided with a wearable physical activity monitor with a visible heart rate display. Importantly, the data from these devices are downloaded wirelessly to a computer and/or mobile device, which then automatically updates their physical activity profile on their personal web-page. Our research study coordinator will receive permission to access each subject's physical activity profile, enabling us to assess their compliance remotely. The data reported on the website includes a 24-hr profile of heart rate and calories expended, allowing us to clearly distinguish compliance to the HIIT regimen. We will assess each subjects' physical activity profile on a weekly basis and record how many prescribed exercise sessions were successfully completed. If participants do not have access to the appropriate technology, we will make alternative arrangements such as providing them with an inexpensive mobile device with the necessary technology, providing a recordable heart rate monitor to wear during exercise, or collecting training logs.

- C3.2.2 Routine exercise counseling: Patients receive counseling regarding exercise as a routine part of their participation in the bariatric surgery clinic. Specifically, they are counseled to participate in 60 min of aerobic exercise daily in addition to 2-3 non-consecutive days of strength training workouts every wk. Patients are encouraged to contact the bariatric conditioning program, obtain a gym membership, purchase exercise equipment, join a walking group, and/or sign up for fitness classes (employer or city parks and recreation).

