| Anthropometric measures^ | | X | X | X | X |
| Orthostatic Hypotension Assessment [^] | | Х | X | X | Х |
| Quality of Life measures: | | | | | |
| NeuroQol | | X | X | X | X |
| Questionnaires | | X | Х | Х | X |
| Demographics | | X | | | |
| Functional Assessments | | | , . | , . | |
| Berg Balance Scale [^] | | X | X | X | X |
| 8-foot Get Up and Go Test^ | | X | X | X | X |
| Modified Falls Efficacy Scale | | Х | X | Х | Х |
| Aerobic Assessment | | | | | |
| VO2 max | X | | | | X ⁺ |
| | | | | | |
| Dual Energy X-ray Absorptiometry | | | | | |
| Duai Lineigy A-iay Absorptionietry | | X | | | X |

^{*}Randomization to exercise protocol to occur after baseline visit

Data collected for clinical purposes as part of the Adult Bariatric Surgery Program will be reviewed as part of this study and included in the study records.

- **C3.6. Timeline and milestones:** The planned study duration is 5 yr, with 2 yr of subject accrual, 2 yr of subject follow-up, plus 1 yr for analysis and results presentation.
- **C3.7. Statistical analysis:** The four treatment groups (HIIT/no surgery, HIIT/surgery, routine exercise/no surgery, routine exercise/surgery) will be compared with respect to demographic and baseline variables (e.g., age, sex, glycemic status, OGIS, BMI, etc.). If a significant difference is found in any variable, the models described below will be fitted after adjusting for these variables.
- C3.7.1 Analysis of primary outcome: The primary outcome is IENFD at the proximal thigh, measured at baseline, 3, 12, and 24 mo. Exploratory analysis will be performed to assess the need for any transformation

^{*}Only participants randomized to the HIIT will complete a second time

 $^{^{\}mathsf{T}}$ Participants can consent to have skin biopsy added to biorepository

[^]Participants may complete the consent and outcomes virtually prior to the upcoming visit to decrease in-person interaction due to Covid-19. If the outcome cannot be completed successfully it with be completed during the visit.

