where β_{00} is the population-averaged intercept, Z_i is the matrix of main effects and interaction corresponding to HIIT exercise and bariatric surgery, \underline{X}_{it} is the matrix of fixed covariates (demographic and baseline characteristics), λ and θ are the vectors of corresponding fixed effects parameters, β_{0i} is the subject-specific random (intercept) effect capturing heterogeneity across subjects due to unmeasured confounders, and en is the random error characterizing variation due to sources like within-subject fluctuations and measurement error. The random effect β_{0i} is assumed to follow a normal distribution with mean zero and variance σ^2_{sub} , and the eit's are assumed to be distributed normally with mean **0** and variance covariance matrix R (non-diagonal). Furthermore, we also assume that θ_{0i} and e_{it} are independent. Maximum likelihood method will be used to estimate the model parameters. We will use Akaike Information Criterion (AIC) and Schwarz Bayesian Information Criterion (BIC) to guide the selection of the covariance structure. Inference for λ (which is of primary interest) will be based on Wald tests. We will use PROC MIXED in SAS to fit the above model. To explore potential non-linear or threshold effect of treatment exposure on IENFD we will use a nonparametric regression model fitted using the framework of generalized additive models (GAM). 115 Given the exploratory nature of the research proposed here, the GAM models will allow us the flexibility to include a smooth functional term instead of restricting to a linear relationship. The smoothing term is fitted by using penalized regression splines or locally smoothed loess curves, with the degree of smoothness chosen in a data-adaptive way, using cross-validation techniques. We will use the gam function in the mgcv package available in the R software to fit these non-parametric regression models. We will perform sensitivity analyses to assess how subjects who withdrew affect conclusions of the analysis. An intent-to-treat analysis set (including subjects who are randomized, treated, and have a baseline IENFD) will be used to assess treatment effects, with multiple imputation methods¹¹⁶ employed to impute outcomes for subjects with missing post-baseline data. Depending on the extent and pattern of missingness, other simpler sensitivity analyses may be used: e.g., subjects completing the study (completers) may be analyzed using a repeated measures analysis of variance model. The model will include the same covariates that are included in the primary analysis.

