
C3.7.2 Analyses of secondary outcomes: Due to the pitfalls of multiple testing, formal statistical testing won't be performed. For analysis of repeated measures of continuous data (CCM, cardiovascular reflex tests, MNSI, UENS, mTNS, SAS, McGill Pain questionnaire, NeuroQOL, and functional assessments), the longitudinal approaches described above will be employed. Specifically, each outcome will be analyzed separately using a linear mixed effect regression model, with the treatment group as the primary exposure.

C3.7.3 Exploratory analyses: To investigate the potential modifying effects of sex, we will perform an additional analysis that includes an interaction term between the intervention groups and sex. Similarly, we will explore the differential effect of sleeve gastrectomy versus Rou-en-Y gastric bypass by including separate indicator variables for these two different surgical techniques. We will also investigate the potential weight loss independent effects of bariatric surgery by evaluating the earliest time point (3 months). In addition to other metabolic syndrome components, we will study the effect of change in insulin sensitivity as measured by OGIS on our primary outcome. Finally, we will perform an analysis of those who complete more than 80% of supervised exercise sessions to assess the effect of exercise compliance. Importantly, these analyses will be hypothesis generating for future studies.

C3.8. Power calculation: The purpose of this clinical trial is to provide the preliminary data necessary to design a multicenter clinical intervention trial. Therefore, it is not strictly amenable to formal power

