considerations. However, there are two assumptions necessary to justify the multicenter trial. The first is that HIIT will cause an increase in IENFD (re-innervation) and the second is that the natural progression of DSP is loss of nerve fibers over time. The primary outcome is an assessment of IENFD at the proximal thigh over 4 time points spanning 24 mo in the four trial arms. To estimate the likely effect sizes of the four interventions, we will rely on previous well-conducted studies, including our ongoing NIH K23 project. For the routine exercise/no surgery group, we estimate that the IENFD will decrease similar to that observed for those with pre-diabetes and DSP. Over 26.7 mo, IENFD at the proximal thigh decreased from 19±5 to 13±4. Given that our population includes patients with normoglycemia, we expect a decline of at least 3 fibers/mm over the 2 yr of our study. For the HIIT/no surgery group, we estimate that the IENFD will increase by 1.4±2.3 fibers/mm based on a study of the effect of exercise by Smith et al.³⁰ They saw this effect after 1 yr, but we will conservatively estimate that the effect will plateau after the initial yr after the intervention. For routine exercise/surgery group, we estimate that the IENFD will increase by 0.2±7.0 based on our preliminary data on patients undergoing diet-induced weight loss for 2 yr. For the HIIT/surgery group, we estimate that the effect will be additive compared to the two separate interventions. With our expected sample size of 30 patients (allowing for ~15% attrition) in each of the four treatment groups, we will have at least 80% power to detect effect sizes between 0.9 and 1.7 as statistically significant based on a two-sided test with alpha=0.05.

- **C3.9. Data collection and management:** Data report forms will be filled out during each visit, verified, and entered into RedCap. Validation reports will be run, and checked for omissions, improbable values, and data consistency. Distributions of continuous measures will be assessed for symmetry and transformations will be applied as needed. Co-investigator [name], Professor of Biostatistics, [name], graduate student, and [name] will have data access for monitoring and verification.

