- **C4. Potential problems & alternative approaches for all Aims:** We hypothesize that HIIT will improve DSP outcomes. We also believe that the effect of HIIT will be greater than the effect of bariatric surgery. However, our supportive preliminary data are based on a diet-induced weight loss intervention, and the effect of surgical weight loss may be larger. If surgery is as good as or better than HIIT, the results would still lead us toward one of the first disease modifying therapies for DSP. Our study design is also able to look at the combined effects of HIIT and bariatric surgery. If the severity of DSP is less in our population, the IENFD of the proximal thigh may not be the most sensitive DSP outcomes measure; however, we plan to use IENFD of the distal leg as a secondary outcome measure. In contrast to our supportive preliminary data, if the HIIT regimen is difficult to perform for this obese population, we could switch interventions to a conventional exercise regimen, which [name] has extensive experience with in patients with obesity and diabetes.
- C5. Biorepository to enable future mechanistic studies: We will obtain fasting plasma DNA, urine, skin

biopsies, and subcutaneous adipose tissue samples. While beyond the scope of this current proposal, this biorepository will allow for future studies to better understand the mechanisms by which HIIT and/or bariatric surgery improve DSP outcomes. Which intervention to pursue will be based on which intervention(s) is/are successful at improving DSP outcomes in this clinical trial. Drs. [name] (co-I, HIIT) and [name] (consultant, bariatric surgery) have the expertise to explore mechanisms in humans. As Director of the Obese-Adipose Tissue Research Laboratory, [name] will help obtain and process the subcutaneous adipose tissue obtained for this proposal. [name] (consultant, murine DSP outcomes), in conjunction with Drs. [name] and [name] (consultants, murine bariatric surgery), has the expertise to explore mechanisms in mice. The biorepository will allow translational research from mouse to human and from human to mouse. Our experienced team of investigators and consultants is uniquely positioned to accomplish this goal.

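### The analysis set called intent-to-treat admits only treated subjects, an undefined post-randomisation condition that can remove HIIT non-starters but hardly any controls

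*Protocol*

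**What the plan says.** Section C3.7.1 (Analysis of primary outcome) describes a linear mixed model fitted by maximum likelihood and then announces: "We will perform sensitivity analyses to assess how subjects who withdrew affect conclusions of the analysis". The next sentence defines the only analysis set in the protocol: "An intent-to-treat analysis set (including subjects who are randomized, treated, and have a baseline IENFD) will be used to assess treatment effects". It adds that multiple imputation will fill in missing post-baseline outcomes, and the sentence after that mentions other, simpler sensitivity analyses.

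Four other places bear on this definition:

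- **Timing.** The footnote to Table 6 (C3.5) reads: "Randomization to exercise protocol to occur after baseline visit".
- **Control condition.** Aim 1 in section 2 says: "Routine exercise counseling is the current real world practice in the bariatric surgery clinic". Section C3.2.2 says: "Patients receive counseling regarding exercise as a routine part of their participation in the bariatric surgery clinic".
- **HIIT condition.** Section C3.2.1 requires a week of familiarisation, a ramp-up and then sessions three times a week for 24 months. In the surgery stratum this begins no sooner than 4 weeks after the operation.
- **Compliance.** The only threshold is in the exploratory analyses (C3.7.3): "we will perform an analysis of those who complete more than 80% of supervised exercise sessions to assess the effect of exercise compliance". It is not linked to the word *treated*.

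**The concern.** Intention-to-treat means analysing everyone as randomised, whatever treatment they went on to receive. A set that also requires subjects to have been treated contradicts its own label.

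Such a condition can be tolerated when failing to start cannot depend on the arm, for example with blinded treatment. Here participants know their assignment and the two arms make very different demands. The condition can therefore act on one arm only.

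Aim 1 is the only randomised comparison in the trial. If the set governs the primary model, that comparison is made between all controls and a self-selected part of the HIIT arm. If it governs only the imputation analysis, the check on withdrawals leaves out the HIIT patients who withdraw before starting. Multiple imputation does not repair this, because it acts only on subjects already in the set.

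**Working it through.** **1. Which of the three conditions matters**

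| Condition in C3.7.1 | When it is settled | Can it differ by arm? |
|---|---|---|
| Randomised | At assignment | No |
| Baseline IENFD available | Before assignment (Table 6 footnote) | No |
| Treated | After assignment | Yes: counselling is routine care, HIIT has to be started |

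The word could mean one familiarisation session, one HIIT session or reaching the full regimen. The protocol does not choose between them, and under each of these readings it is the HIIT arm that can lose patients.

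**2. Inputs**

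The protocol gives no figure for the effect of this condition, so there is none to reproduce. From C3.1: 35 per group in four groups, so 70 per exercise arm. From C3.8: about 15% attrition (35 × 0.85 = 29.75, about 30 per group, so 60 per exercise arm) and two-sided alpha 0.05. Expected changes in C3.8 are +1.4 for HIIT/no surgery and −3 for routine exercise/no surgery. For the third group: "For routine exercise/surgery group, we estimate that the IENFD will increase by 0.2±7.0". Assumed, because the protocol is silent: a share *f* = 5%, 10% or 20% of the HIIT arm never starts.

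**3. Dilution: the set compared with all randomised**

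Suppose non-starters follow the control course and the difference among starters is *D*. The all-randomised difference is *D*(1 − *f*), the treated set gives *D*, and the overstatement is *D* × *f*.

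- No surgery: *D* = 1.4 − (−3) = 4.4.
- Surgery, if *additive* in C3.8 means summing the stated changes: 1.4 + 0.2 = 1.6, so *D* = 1.6 − 0.2 = 1.4.
- Surgery, if *additive* means effects relative to control: −3 + 4.4 + 3.2 = 4.6, so *D* = 4.6 − 0.2 = 4.4, as without surgery.

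| *f* | All randomised, *D* = 4.4 | Overstatement, *D* = 4.4 | Overstatement, *D* = 1.4 |
|---|---|---|---|
| 5% | 4.18 | 0.22 | 0.07 |
| 10% | 3.96 | 0.44 | 0.14 |
| 20% | 3.52 | 0.88 | 0.28 |

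(fibers/mm)

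**4. Selection when HIIT has no effect**

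Suppose those who would not start HIIT do *d* SD worse whichever arm they are in. Only those in the HIIT arm are removed. The bias is *f* × *d* SD and the standard error is √(1/*n* + 1/(*n*(1 − *f*))). With *d* = 0.5 and *n* = 70:

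| *f* | Bias (SD) | Standard error | Shift in *z* | Two-sided type I error | Same, *n* = 60 |
|---|---|---|---|---|---|
| 5% | 0.025 | 0.171 | 0.146 | 5.24% | 5.21% |
| 10% | 0.050 | 0.174 | 0.288 | 5.95% | 5.82% |
| 20% | 0.100 | 0.179 | 0.558 | 8.63% | 8.11% |

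A simulation of 20,000 trials per rate (*n* = 70) gave 5.2%, 5.7% and 8.3% for the treated set and 4.6% to 4.9% for all randomised. With *d* = 0.25 the closed form gives 5.1% to 5.9%. A separate calculation with 5% to 15% non-start and gaps of 0.25 to 1 SD gave 5.1% to 13.6%.

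**5. Does deleting the word suffice?**

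In 4,000 simulated trials per rate (no-surgery means, SD 2.3 assumed in both arms, 70 per arm), non-starters who stayed in follow-up gave differences of 4.17, 3.96 and 3.52. When they were lost and imputed from HIIT starters, the difference was 4.40 at every rate, the same as with the treated set. The wording change needs follow-up of non-starters to have any effect.

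**The case against.** The strongest objection is that the sentence probably describes a sensitivity analysis. It follows the announcement of sensitivity analyses, precedes the mention of simpler ones, and the paragraph later speaks of the primary analysis as something separate. No text restricts the population of the mixed model. This is a fair reading. But the set is the only one defined and is the one said to assess treatment effects, so the other reading remains open. Under either, the definition does not do what its label says.

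Secondly, the meaning of *treated* might be settled in a statistical analysis plan. That answers the missing definition. It does not answer the contradiction, since any definition still makes inclusion depend on what happens after randomisation.

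Thirdly, the size is assumed throughout. This stands. A 20% non-start rate exceeds the whole planned attrition of about 15%, and patients must accept random assignment and pass a stress test before entry, which makes never starting less likely. At 5% the type I error is practically nominal. The dilution figures are a gap between two estimands, not a bias under the null, and they use the protocol's own large expected difference.

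Fourthly, C4 does consider what to do "if the HIIT regimen is difficult to perform for this obese population", but that is a contingency for the whole trial, not a statement about individuals who never start. The point does not depend on it.

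Finally, the trial is meant to supply preliminary data. That limits the consequences. It does not justify the definition, because the result is to decide which intervention goes to phase 3.

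**Conclusion.** The concern holds and should be fixed. The protocol calls a set intent-to-treat while making membership depend on an undefined event after randomisation, one that controls meet almost automatically and HIIT patients can fail. This is an error in the text as written, not a detail left for later.

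Its size cannot be derived from the protocol. The overstatement of 0.22 to 0.88 fibers/mm without surgery assumes 5% to 20% non-starters who follow the control course. The type I error of 5.2% to 8.6% assumes the same rates and a 0.5 SD worse outcome in non-starters. There is no bias under the null if non-starters do not differ, and its sign reverses if they do better. The effect is small if few fail to start, but it cannot be bounded while *treated* is undefined. These figures affect the main result only if the set governs the primary model; otherwise they affect the imputation analysis.

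**What to change.** In C3.7.1:

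1. Delete *treated*. Define the set as all randomised participants with a baseline IENFD, analysed by assigned exercise arm whether or not HIIT was started.
2. State that both the primary mixed model and the multiple imputation use this set.
3. State that patients who never start HIIT keep their 3, 12 and 24 month outcome visits. Otherwise imputation under missing-at-random draws their values from HIIT starters and reproduces the treated-set result.
4. If a treated set is wanted, keep it as a labelled supplementary analysis with the term defined for both arms. The compliance question already has its own exploratory analysis in C3.7.3.

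The cost is one or two sentences and the effort of retaining non-starters at visits already scheduled. Planned enrolment and the stated power calculation do not change. The HIIT estimate may come out slightly less favourable.
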